### Adverse Event Expedited Reporting System (AdEERS)

An electronic system for expedited submission of AE reports.

### Attribution

The determination of whether an AE is related to a medical treatment or procedure. Attribution categories:

**Table 3. Relationship of Study Drug To Adverse Event**

Relationship	Description
Definite	A clinical event in which a relationship to the use of the study drug seems definite because of such factors as consistency with known effects of the drug; a clear temporal association with the use of the drug; lack of alternative explanations for the event; improvement upon withdrawal of the drug (de-challenge); and recurrence upon resumption of the drug (rechallenge). Thus, the AE is clearly related to the study drug.
Probable	A clinical event in which a relationship to the study drug seems probable because of such factors as consistency with known effects of the drug; a reasonable temporal association with the use of the drug; lack of alternative explanations for the event; and improvement upon withdrawal of the drug (de-challenge). Thus, the AE is likely related to the study drug.
Possible	A clinical event occurring coincident with administration of the study drug and which is not likely to be explained by concurrent disease or other drugs or chemicals. Information on drug withdrawal may be lacking. Thus, the AE may be related to the study drug.
Unlikely	A clinical event with a temporal relationship to study drug administration that makes a causal relationship improbable and in which other factors suggesting an alternative etiology exist. Such factors include a known relationship of the adverse event to concomitant drug, the subject's disease state, or environmental factors including common infectious diseases. Thus, the AE is doubtfully related to the study drug.
Unrelated	A clinical event, including a laboratory test abnormality, in which a relationship to the study drug seems improbable because of factors such as inconsistency with known effects of the study drug; lack of a temporal association with study drug administration; lack of association of the event with study drug withdrawal or rechallenge; and/or presence of alternative explanations for the event. Alternative explanations might include a known relationship of the adverse event to a concomitant drug, past medical history of a similar event, the subject's disease state, or environmental factors. Thus, the AE is clearly NOT related to the study drug.

An AE is considered to be related to study drug treatment if the causality assessment is ranked as possible, probable, or definite.

## 6.2 Expedited AE Reporting Procedures

Expedited AE reporting for this study must use AdEERS, accessed via the CTEP home page (<http://ctep.cancer.gov>). The reporting procedures to be followed are presented in the CTEP, NCI Guidelines: Adverse Event Reporting Requirements which can be downloaded from the CTEP home page (<http://ctep.cancer.gov>). These requirements are briefly outlined in the table below.

In the rare occurrence when internet connectivity is lost, an AE report may be submitted using CTEP's Adverse Event Expedited Report-Single Agent or Multiple Agent paper template (available at <http://ctep.cancer.gov>) and faxed to the AMC Operations Center at [contact]. A 24-hour notification is to be made to AMC by telephone at [contact], only when internet connectivity is disrupted. Once internet connectivity is restored, an AE report submitted on a paper template, or a 24-hour notification phoned in, must be entered electronically into AdEERS by the original submitter at the site.

AdEERS is programmed for automatic electronic distribution of reports to the following individuals: Protocol Chair, Principal Investigator at the local AMC treating institution, the PTC Therapeutics Medical Monitor and AMC Operations Center. AdEERS provides a copy feature for other e-mail recipients.

### 6.2.1 Expedited Reporting Requirements for AEs that occur within 30 Days of Last Protocol Treatment (Investigational Agent)

**Table 4. Expedited Reporting Timelines for Investigational Agents**

Grade	1	2	2	3		3		4 & 5 1	4 & 5 2
	Unexpected and Expected	Unexpected	Expected	Unexpected		Expected		Unexpected	Expected
				with Hospitalization	without Hospitalization	with Hospitalization	without Hospitalization		
Unrelated Unlikely	Not Required	Not Required	Not Required	10 Calendar Days	Not Required	10 Calendar Days	Not Required	10 Calendar Days	10 Calendar Days
Possible Probable Definite	Not Required	10 Calendar Days	Not Required	10 Calendar Days	10 Calendar Days	10 Calendar Days	Not Required	24-Hour; 5 Calendar Days	10 Calendar Days

 Adverse events with attribution of possible, probable, or definite that occur greater than 30 days after the last dose of treatment require reporting as follows:

- 24-hour notification followed by complete report within 5 calendar days for:
  - Grade 4 and Grade 5 unexpected events
- Complete SAE report within 10 calendar days:
  - Grade 3 unexpected events with hospitalization or prolongation of hospitalization
  - Grade 5 expected events

 Although 24-hour notification is not required for death clearly related to progressive disease, a full report is required as outlined in the table.

December 15, 2004

6.2.1.1 Note: All deaths on study require both routine and expedited reporting regardless of causality. Attribution to treatment or other cause must be provided.

6.2.1.2 Expedited AE reporting timelines defined:

“24 hours; 5 calendar days”– The Investigator must initially report the AE via AdEERS, according to the procedures outlined in section 6.2, within 24 hours of learning of the event, and followed by a complete AE report submitted via AdEERS within 5 calendar days of the initial 24-hour report. Use the NCI protocol number and protocol-specific subject ID assigned during trial registration on all reports.

“10 calendar days”– A complete AdEERS report on the AE must be submitted within 10 calendar days of the Investigator learning of the event. Use the NCI protocol number and protocol-specific subject ID assigned during trial registration on all reports.

Any medical event equivalent to CTCAE Grade 3, 4, or 5 that precipitates hospitalization (or prolongation of existing hospitalization) must be reported regardless of attribution and designation as expected or unexpected with the exception of any events identified as protocol-specific expedited AE reporting exclusions.

Any event that results in persistent or significant disabilities/incapacities, congenital anomalies, or birth defects must be reported via AdEERS according to the guidelines as described above.

All expedited reports should be submitted to the local IRBs according to local IRB policies and procedures.

### **6.3 Routine AE Reporting**

AEs reported through AdEERS must also be reported in routine study data submissions. Routine reporting of all AEs, regardless of grade, should be reported on the Adverse Event Form CRF.

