PTC299 was well tolerated and there were no serious drug-related adverse events. Among the 40 subjects dosed in Stage 1, the most frequent treatment-emergent adverse events were headache (nine episodes in eight subjects, all receiving PTC299) and nausea (five episodes in five subjects, four receiving PTC299 and one receiving placebo). Other types of adverse events occurred in fewer than five subjects (10%). During Stage 2, the most frequent adverse events were headaches (three episodes in three subjects)

and back pain (two episodes in two subjects); other adverse events were noted only in single subjects. All adverse events were Grade 1 in severity, except one case of Grade 2 diarrhea in a subject receiving 1 mg/kg of PTC299 in the fasted state in Stage 2. The incidence, relationship to study drug, and severity of adverse events were not clearly dose dependent, although the number of headaches may have increased slightly with dose. No deaths or serious adverse events occurred during the study. No subject prematurely terminated the study for safety reasons.

In both stages, there were no safety concerns based on subjects' physical examinations, vital sign measurements, or ECGs. No clinically significant changes in hematology, coagulation, or chemistry parameters were observed. Similarly, no clinically meaningful urinalysis abnormalities were seen.

[figure not shown]
Mean plasma concentration-time profiles for PTC299 during Stage 1 are shown in Figure 1 below. Mean plasma concentration-time profiles for PTC299 according to fed or fasted status of subjects are shown in Figure 2 below. PTC299 appeared in plasma after a lag time of ~30 minutes. At body-weight-adjusted (mean total) doses  $\geq 0.30$  (24 mg) mg/kg, PTC299 concentrations persisted in plasma through 72 hours and, at the 3.0-mg/kg (203 mg) dose, low concentrations of PTC299 were still evident at 168 hours after drug administration. The mean  $C_{max}$  was increased in subjects when they received the drug after a high-fat, high-calorie meal. With or without food, the target plasma concentration of 0.10 to 0.15  $\mu\text{g/mL}$  established in animal tumor models was safely achieved.

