## 4.0 CLINICAL AND LABORATORY EVALUATIONS

All signs, symptoms, HIV-related and AIDS-defining events (refer to Appendix XII), death and toxicities must be documented. All signs, symptoms and laboratory results  $\geq$  Grade 2 that are felt to be clinically significant or drug-related and all HIV-related and AIDS-defining events and deaths must be recorded on the case report forms (CRFs).

All prescription medications taken within 14 days prior to study enrollment and during the interval between each visit must be recorded on CRFs. The duration of all anti-HIV medications and all opportunistic infection (OI) treatment and/or prophylaxis medications at the time of enrollment must be recorded in the CRF. All non-prescription medications must be recorded in the clinic record.

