**Table 5. PTC Therapeutics Serious Adverse Event Regulatory Reporting Requirements**

Type of Event			Type of Report	Timeframe for Reporting To Health Authorities
Fatal or Life-Threatening	Unexpected	Related		
Yes	Yes	Yes	Telephone/Fax notification or report	Within 7 calendar days of PTCAD or according to local regulations
			FDA Form 3500A or CIOMS I form	Within 15 calendar days of PTCAD or according to local regulations
No	Yes	Yes	FDA Form 3500A or CIOMS I form	Within 15 calendar days of PTCAD or according to local regulations
Yes	No	Yes	Annual report	Annually
No	No	Yes		
Yes	Yes	No		
No	Yes	No		
Yes	No	No		
No	No	No		

a. Includes possibly or probably related events

Abbreviations: CIOMS I = Council for International Organizations of Medical Sciences, FDA = Food and Drug Administration, PTCAD = PTC Therapeutics Awareness Date

If notification of an adverse event requiring expedited reporting is received, PTC Therapeutics will contact each investigator using PTC299 by e-mail or regular mail within 15 working days from the PTCAD such that the Investigator can promptly notify the site IRB. A complete written report will follow the initial notification. PTC will receive all SAE notifications via AdeERS. Although AdeERS reports are automatically forwarded to the FDA, PTC will maintain responsibility for ensuring all events are reported to the FDA according to federal requirements according to the Regulatory Reporting Requirements listed in Table 5 above. Routine reporting of all AEs will be recorded by the sites on the Adverse Event Form CRF.

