Immunohistochemistry (IHC) will be used to determine expression of the following: VEGF, VEGFR-2, VEGFR-3, phospho-Akt, KSHV LANA, orf59, p53 and HIF-1 $\alpha$ . We will count the number of positive cells per HPF for a total of 10 fields per section and derive an index value. We will consider a 50% change from baseline in the index value for the aforementioned markers a biological response. For each measure (VEGF, VEGFR-2, VEGFR-3, phospho-Akt, KSHV LANA, orf59, p53 and HIF-1 $\alpha$ ), we will estimate the proportion of patients who demonstrate a 50% change between baseline and on treatment (between day 22 and day 28) value. The exact binomial 95% confidence interval will be derived for each measure.

To evaluate the effects of PTC299 on tumor cell proliferation, the change in immunohistochemistry of Ki67 from the pre-treatment to the post-treatment biopsy will be tested using the Wilcoxon sign test to determine if the change is less than zero, suggesting a decrease. To evaluate the drug's effects on circulating concentrations of angiogenic factors and cytokines, HIV and KSHV loads, and T-lymphocyte subsets, changes in these levels from pre-treatment to indicated sampling times will be tested by repeated-measures ANOVA, single and multivariate analysis.

For each subject, study drug administration will be described in terms of the actual doses administered and the proportion of drug actually delivered relative to the amount that should have been delivered. The total number of cycles administered; the median (range) of cycles administered; dose modifications, dose delays, and dose omissions; and reasons for deviations from planned therapy will be described by starting dose level. The type and timing of use of concomitant drugs will also be described.

AEs and laboratory abnormalities will be summarized by type and severity grade. First-cycle DLTs, adverse events leading to death or to discontinuation from treatment, and serious adverse events will be considered with special attention.

Pharmacokinetic parameters will be calculated using the actual sample collection times. Pharmacokinetic variables will be calculated from the plasma concentration data using standard compartmental and noncompartmental methods, as appropriate for the data. Variables of interest may include  $T_{max}$ ,  $C_{max}$ ,  $C_{24h}$ ,  $AUC_{0-24}$ , and  $t_{1/2}$ . Plasma concentrations and PK parameter results will be presented in tabular and graphic form by dose level and

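### Section 4.0 sets a threshold for CRF entry of signs, symptoms and laboratory results, Sections 6.3 and 6.4 require every AE, and nothing says which rule governs

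*Combined protocol and SAP*

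**What the plan says.** Section 4.0 (Clinical and Laboratory Evaluations) makes two statements. The first concerns documentation in general: "All signs, symptoms, HIV-related and AIDS-defining events (refer to Appendix XII), death and toxicities must be documented". The second concerns the case report forms and is narrower. It covers signs, symptoms and laboratory results at or above "Grade 2 that are felt to be clinically significant or drug-related", and adds HIV-related and AIDS-defining events and deaths with no grade limit.

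Section 6.3 (Routine AE Reporting) has no such limit: "Routine reporting of all AEs, regardless of grade, should be reported on the Adverse Event Form CRF". Section 6.4, in the text below Table 5, repeats the rule without mentioning grade: "Routine reporting of all AEs will be recorded by the sites on the Adverse Event Form CRF".

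Section 6.1 defines an AE broadly. Unfavorable signs, symptoms, diseases and abnormal laboratory findings all count, whatever their attribution.

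The planned analysis in Section 11.2 is descriptive and states no minimum grade: "AEs and laboratory abnormalities will be summarized by type and severity grade".

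**The concern.** Because of the definition in Section 6.1, the two rules cover the same kinds of event. Section 4.0 filters by grade and by the site's judgment of significance or relatedness; Sections 6.3 and 6.4 do not filter. Section 4.0 also separates what is documented from what goes on the CRF, a distinction that has a purpose only if some documented events stay off the CRF. A site could therefore reasonably read it as a threshold.

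Defining safety and toxicity is the first primary objective (Section 2.1.1), and the AE tables serve it directly. The trial is open to all AMC sites (Section 3.4), and dose-escalation cohorts have three to six subjects. If sites read the rule differently, low-grade counts at a dose level could reflect which sites enrolled there as well as the drug. In addition, the AMC Medical Monitor's quarterly review uses listings of reported events (Appendix X), so an event that is never entered may not reach central review.

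**Working it through.** No arithmetic applies, because the plan attaches no figure to this point. The check sets the sections side by side.

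**Step 1: what each rule requires on the CRF.**

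| Class of event | Section 4.0 | Sections 6.3 and 6.4 |
|---|---|---|
| Grade 1 AE, not HIV-related or AIDS-defining | Not required | Required |
| Grade 2 or higher AE, judged significant or drug-related | Required | Required |
| Grade 2 or higher AE, judged neither, and not HIV-related, AIDS-defining or fatal | Not required | Required |
| HIV-related or AIDS-defining AE, or death, at any grade | Required | Required |

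The rules diverge in the first and third rows only.

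**Step 2: is there a tie-breaker?** None was found. Neither rule refers to the other. Section 4.0 uses *must*, Section 6.3 *should* and Section 6.4 *will*, so the verbs do not settle it. Section 10.1 leaves CRF instructions to the AMC Operations Center, and those instructions are not part of these documents.

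**Step 3: does another reading of Section 4.0 remove the conflict?** The grade limit could be read as applying to laboratory results alone. The significance-or-relatedness condition would remain, and Sections 6.3 and 6.4 have no counterpart to it.

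**Step 4: which outputs are exposed?**

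- DLTs and the MTD: largely protected. Section 5.3.3 requires the investigator to decide DLT status for each subject at the end of every cycle and to record it on the Adverse Event CRF. The graded DLT criteria start at Grade 2 or higher.
- Deaths: required under both rules.
- Events reported through AdEERS: Section 6.3 requires these in routine data as well. Under Section 6.2.1 they include Grade 3 events with hospitalization and Grade 4 and 5 events, regardless of attribution.
- AE and laboratory summaries by type and grade in Section 11.2: exposed, in the Grade 1 counts and in the Grade 2 or higher events judged neither significant nor related.

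**Step 5: can the loss be sized?** No. The documents give no rate for these two classes in patients with HIV-associated KS, and no information on which rule sites followed.

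**The case against.** The strongest reply is that the sections can be read together. Section 4.0 says what must be recorded. It does not say that nothing else may be, so it can stand as a floor, with Sections 6.3 and 6.4 requiring the rest. The chapter devoted to AE reporting states the all-AE rule twice and names the form, whereas Section 4.0 speaks of case report forms in general. Monitoring visits compare AE reporting with source documents (Appendix X), and Section 4.0 requires full documentation, so omissions could be found. The judgment in Section 4.0 is also an either-or test: a Grade 2 or higher event that is clinically significant but judged unrelated is kept.

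Much of this stands. A reader might infer that a site following Section 4.0 alone complies with the protocol. It does not, because Sections 6.3 and 6.4 bind every site. A reader might also infer that the whole primary safety dataset depends on which section a site follows. Step 4 of the working shows that the exposure is confined to two classes of event.

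A reader might also estimate the loss from the single-dose healthy-volunteer study in Section 1.2.6.1, which reports "All adverse events were Grade 1 in severity, except one case of Grade 2 diarrhea". A Grade 2 threshold would have kept at most one of those events. That shows how such a filter behaves when toxicity is mild. It does not predict capture in patients with HIV and KS dosed daily for up to 48 weeks, and it says nothing about site practice, so it does not support a claim that low-grade capture would fall to near zero at some sites.

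The reply does not remove the conflict. The floor reading has to be inferred, the split between documenting and recording points the other way, and monitors are left with two standards against which to check.

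**Conclusion.** The protocol states two different rules for entering the same events on the CRF and does not say which prevails. This is a conflict between stated rules, not a missing detail, and it should be corrected. Its reach is limited to Grade 1 AEs, and to Grade 2 or higher AEs judged neither significant nor related that are not HIV-related, AIDS-defining, fatal or reported through AdEERS. For these, the Section 11.2 summaries could mix full and filtered capture. No hypothesis test or decision rule in the plan uses those rows, and the dose-finding and response conclusions do not rest on them.

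The size of the effect cannot be calculated from the documents. The conclusion assumes that at least some sites treat Section 4.0 as a threshold. If every site enters all AEs, the tables are complete and only the wording needs repair. The Operations Center's CRF instructions may already settle the matter in practice, but they cannot be checked here.

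**What to change.** Amend the CRF sentence in Section 4.0 so that all AEs, of any grade and attribution, go on the Adverse Event CRF, and cross-refer to Sections 6.3 and 6.4. If a threshold is intended, for example for laboratory values, state it identically in Sections 4.0, 6.3 and 6.4, and limit the Section 11.2 tables to what all sites collect.

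Section 3.3.1 reports that three cohorts of three subjects (Stage 1) and a further eight subjects (Stage 2) have already been enrolled, so 9 + 8 = 17 of at most 38 evaluable subjects were entered under the present wording. Before these data are pooled with Stage 3, the sponsor should establish which rule sites applied. If practice differed, the AE tables should say so.

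The cost is one amended sentence, or a few if a threshold is kept, and slightly more data entry at sites now using the filter. The check on practice to date needs a query to sites.

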### **6.4 PTC Therapeutics Adverse Event Reporting Requirements**

Each SAE reported through AdEERS received from AMC sites must be evaluated by the Investigator, the AMC medical monitor, and the PTC Therapeutics medical monitor. The medical monitors are required to review all unanticipated problems involving risk to subjects or others, serious adverse events, and all subject deaths associated with the protocol and provide an unbiased written report of the event. At a minimum, the medical monitors should comment on the outcomes of the event or problem, and in the case of a serious adverse event or death, comment on the relationship to participation in the study. The medical monitors should also indicate whether they concur with the details of the report provided by the AMC clinic site investigator.

For regulatory reporting purposes, the event is classified as related if the AMC clinic site investigator, the AMC medical monitor, or the PTC Therapeutic medical monitor determines that the event is definitely, possibly or probably related to the study drug. An AE will be considered expected if the protocol or Investigator Brochure indicates that such an event of similar or greater severity has already been observed in association with use of the study medication.

The PTC Therapeutics Awareness Date (PTCAD) is used in determining AE regulatory reporting timelines. The PTCAD is defined as the earliest date PTC Therapeutics or an agent becomes aware of an AE. This is the date the regulatory reporting clock begins.

PTC Therapeutics SAE regulatory reporting requirements are described in the table below.

